5.2 Study Procedures

After consent, the endoscopist will perform a standard of care colonoscopy. We will enroll 54 participants in the study and expect approximately 40 of these participants to have polyps. If a polyp is found, then OCT will be used to image that polyp. Patients with polyps, regardless of number found, will have either one tubular adenoma (NICE type 2) imaged OR one hyperplastic polyp (NICE type 1) imaged. These polyps can be distinguished endoscopically using the NICE classification (see Section 12, Figure 1). If no polyps are found, then one area of normal mucosa will be imaged. We will have a goal of imaging an equal number of tubular adenomas and hyperplastic polyps. We will have a running log of the number of imaged tubular adenomas and hyperplastic polyps imaged to ensure that equal amounts of each type are imaged. If on the rare chance a malignant appearing colonic tumor (NICE type 3) is found, this and no other polyps will be imaged with OCT.

Duration of using OCT probe as well as duration of the colonoscopy will be kept by endoscopy staff with a stopwatch. Initiation of colonoscopy will be time 00:00. There will then be time marks for initiation of OCT imaging, end of OCT imaging, and end of colonoscopy. In this way, the exact duration of OCT and the full duration of colonoscopy with OCT will be captured.

Duration of OCT imaging will be from the time of guiding the OCT probe through the colonoscope to imaging, and withdrawal of OCT probe. The maximum time allotted to obtain OCT imaging will be 10 minutes. Any OCT imaging that reaches the 10-minute mark will be stopped so that routine colonoscopy can resume. A log of total procedure duration is kept for every standard of care colonoscopy.

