10.3 Sample Size Calculation

The sample size calculation is based on the primary endpoint of feasibility only. The primary hypothesis is that the proportion of the patients who have OCT imaging which adds 5 minutes or less to the duration of standard of care colonoscopy is greater than 75%. The null hypothesis for feasibility is 75% and the alternative hypothesis is 90%. $H_0: p < 75\%$ $H_a: p > 75\%$ (expect it to be 90% in clinical practice). A sample size of 54 patients achieves 80.1% power to detect a difference of 15% using a two-sided exact test at a significance level of 5% with the assumption that the proportion is 75%.

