10.6 Early Stopping Rules

Toxicity, defined as study-related grade 3-5 SAEs, will be reviewed on a continuous basis. Early stopping will be based on the toxicity rate (TR) using the repeated significance testing of Pocock boundary with 80% power and 0.05 overall Type I error. We assume that no more than 5% is acceptable and a maximum-tolerated TR is 30%. The study will be halted if a study-related grade 3-5 SAE occurs in the first 2 patients, or 2 of the first 8 patients, or 3 of the first 15 patients, or 4 of the first 24 patients, or 5 of the first 34 patients,

or 6 of the first 45 patients. R function-toxbdry was used for calculations.

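### The toxicity stopping rule in 10.6 ends at patient 45 of a planned 54, so no event among the last nine patients can trigger it; the effect is small.

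*Combined protocol and SAP*

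**What the plan says.** Section 10.6: "Toxicity, defined as study-related grade 3-5 SAEs, will be reviewed on a continuous basis". The boundary is described as derived "using the repeated significance testing of Pocock boundary with 80% power and 0.05 overall Type I error", with 5% as the acceptable toxicity rate and 30% as the maximum tolerated. Six halting conditions follow: an event in the first 2 patients, then 2 of 8, 3 of 15, 4 of 24, 5 of 34, and finally "or 6 of the first 45 patients". The text names the R function toxbdry but not the maximum sample size given to it.

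Section 5.2: "We will enroll 54 participants in the study". Section 10.3 derives the same number: "A sample size of 54 patients achieves 80.1% power to detect a difference of 15% using a two-sided exact test". Section 5.3 makes every patient imaged with the probe evaluable for toxicity. No section gives a condition for patients 46-54, a general formula that would yield one, or a statement that the rule lapses at 45.

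**The concern.** A rule said to apply continuously should have a threshold at every patient up to the planned maximum. Here 54 - 45 = 9 patients, one sixth of the study, are enrolled with no threshold in force. The rule is also inconsistent in its own terms: a higher event proportion after patient 45 lets the study continue, where a lower one at patient 45 would have halted it. At stake is whether the written rule, followed literally, would respond to a late cluster of serious events in an early feasibility study of a device. A related point is whether the six-monthly report, which section 9.0 says must set the stopping rules against supporting data, would have any rule to apply to those patients.

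**Working it through.** **Inputs.** Boundary, 5% and 30% rates, stated 0.05 error and 80% power: section 10.6. Planned number 54: sections 5.2 and 10.3. True rates of 10%, 15% and 20% are my assumption, to cover the range between the plan's two rates.

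**1. Coverage.** Write t(n) for the number of events that halts the study at patient n: 1 for n = 1-2, 2 for 3-8, 3 for 9-15, 4 for 16-24, 5 for 25-34, 6 for 35-45, and undefined for 46-54. The probability of a halt triggered at patients 46-54 is exactly 0 at any true rate.

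**2. A reachable example.** The study can stand at five events at patient 45 without a halt, provided the fifth came after patient 34 and the earlier limits were respected. Events in patients 46 and 47 then give 7/47 = 14.9%, with no halt; 6/45 = 13.3% halts. At the extreme, nine events in the last nine give (5 + 9)/54 = 14/54 = 26%, still with no halt.

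**3. Is seven events after patient 45 beyond the listed boundary?** The binomial tail at 5% is P(X ≥ 6 | n = 45) = 0.0239 and P(X ≥ 7 | n = 54) = 0.0176. Seven events by any patient from 47 to 54 is therefore stronger evidence against 5% than the last result that the rule treats as a halt.

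**4. The stated error rate.** Let S(n,k) be the probability of being unhalted after n patients with k events. Then S(n,k) = (1-p)·S(n-1,k) + p·S(n-1,k-1) for k < t(n), and P(halt at n) = p·S(n-1, t(n)-1). Summed over n at p = 0.05, the overall type I error is 0.159. If the first entry is read as 2 of 2, it is 0.096. The stated 0.05 is not reproduced, and setting the maximum to 45 does not recover it (0.159 again). This can be checked by hand:
- First entry alone: 1 - 0.95² = 0.0975.
- 2 of 8 alone: 1 - 0.95⁸ - 8(0.05)(0.95⁷) = 1 - 0.6634 - 0.2793 = 0.057.

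Either reading has passed 0.05 by patient 8. At p = 0.30 the probability of a halt is above 0.998 on both readings, against the stated 80%.

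**5. What the missing stretch is worth.** As an illustration, not a proposed rule, keep the six entries and set t(n) = 7 for n = 46-54:

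| True rate | First entry as 1 of 2: P(halt) written → extended | First entry as 2 of 2: P(halt) written → extended | Gain (points) | Mean patients spared |
|---|---|---|---|---|
| 5% | 0.159 → 0.162 | 0.096 → 0.099 | 0.25-0.28 | about 0.006 |
| 10% | 0.489 → 0.517 | 0.433 → 0.465 | 2.8-3.2 | 0.07-0.08 |
| 15% | 0.798 → 0.836 | 0.774 → 0.817 | 3.8-4.3 | 0.10-0.12 |
| 20% | 0.946 → 0.966 | 0.939 → 0.962 | 2.0-2.2 | 0.06-0.07 |
| 30% | 0.9986 → 0.9996 | 0.9984 → 0.9995 | 0.1 | about 0.004 |

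The gain is small because few studies with a high event rate get that far. On the literal reading of the first entry, the probability of passing patient 45 unhalted is 84.1% at 5%, 51.1% at 10%, 5.4% at 20% and 0.14% at 30%.

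**6. Timing.** Section 10.4 expects 5-10 participants per day, so nine patients take about 9/10 = 0.9 to 9/5 = 1.8 days. Section 5.2 collects events by telephone at about 48 hours. The table assumes each outcome is known before the next patient is imaged, so the patients spared are an upper figure.

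**The case against.** The strongest reply is that the gap hardly matters at the two rates the plan names. Extending the list moves the halt probability by under 0.3 points at 5% and by about 0.1 at 30%, and most of the added halts at the lower rates come at patients 51-54, when almost everyone has been imaged. With fast accrual and 48-hour calls, even a complete boundary might act too late to spare anyone. Section 9.0 also has the principal investigator and coordinator watch for serious toxicity throughout, and Appendix B requires expedited reporting of unanticipated problems. All of this stands and keeps the point minor. It does not close the gap, because neither provision contains a numerical halting criterion.

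Three stronger readings are tempting, and the documents do not support them:
- A reader might infer that 7 of 46 would escape the rule. It cannot: seven events in 46 patients means at least six in the first 45, which already halts. The earliest unhalted seven-event record is 7 of 47.
- A reader might infer that the last nine patients are unmonitored. They are monitored and remain evaluable for toxicity; only the numerical rule is absent.
- A reader might infer that the calculation was run with a maximum of 45, or that appending one entry restores the stated design. The plan does not state the maximum used, and the listed entries already exceed 0.05 without any addition.

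**Conclusion.** The point holds as a minor one. The written rule is silent for patients 46-54, and its last entry halts a record less extreme than some that it would let continue. The largest loss among the rates checked is about 4 points of halt probability, at a true rate of 15%; at 5% and 30% the loss is negligible. These figures rest on independent events with a constant rate, immediate reporting, 54 patients imaged, and an illustrative seventh-event threshold. Ranges cover both readings of the first entry. They come from an exact recursion on the listed boundary; toxbdry itself was not run. The mismatch between the listed boundary and its stated 0.05 error is a separate and larger matter in the same paragraph, and it governs how the gap should be closed.

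**What to change.** Reconcile section 10.6 with the planned 54. Recalculate the boundary by the stated method and rates at a maximum of 54, state that maximum, say whether the first entry means one or two events, list the thresholds through patient 54, and report the exact crossing probabilities at 5% and 30%. No change to the tolerated rates is suggested.

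The cost is one recalculation and a short edit to 10.6, but the edit may not be confined to the last line: a recalculation that truly held 0.05 could alter earlier entries. If instead only the last stretch were added to the existing list, the downside would be under 0.3 points more false halts at 5%. The overall type I error would then remain at about 0.162 (0.099 with the first entry as 2 of 2), and the stated 0.05 would still need correcting.

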12.0 FIGURES

Figure 1. The OCT fiber probe laser focusing structure is depicted in Fig. 2. It is composed of a lead-in single mode fiber (SMF), a no-core fiber (NCF) for laser expansion, and a segment of gradient index (GRIN) fiber for laser focusing. The diameter of the GRIN fiber can be changed to realize different resolutions and working distances. The working distance is defined as the distance between the laser focus and the GRIN fiber end-face. In our experiments, GRIN fiber with a 230 μm diameter is used to realize a resolution of around 25 μm and a working distance of around 1.8 mm in air. The lengths of the GRIN fiber and NCF are 1300 μm and 400 μm , respectively.

[figure not shown]
[figure not shown]
[figure not shown]
[figure not shown]
[figure not shown]

Figure 2. Colonoscope instrument channel.

NBI International Colorectal Endoscopic (NICE) Classification*

[figure not shown]
	Type 1	Type 2	Type 3
Color	Same or lighter than background	Browner relative to background (verify color arises from vessels)	Brown to dark brown relative to background; sometimes patchy whiter areas
Vessels	None, or isolated lacy vessels coursing across the lesion	Brown vessels surrounding white structures**	Has area(s) of disrupted or missing vessels
Surface Pattern	Dark or white spots of uniform size, or homogeneous absence of pattern	Oval, tubular or branched white structure surrounded by brown vessels**	Amorphous or absent surface pattern
Most likely pathology	Hyperplastic	Adenoma***	Deep submucosal invasive cancer
Examples			
			

* Can be applied using colonoscopes with or without optical (zoom) magnification

** These structures (regular or irregular) may represent the pits and the epithelium of the crypt opening.

*** Type 2 consists of Vienna classification types 3, 4 and superficial 5 (all adenomas with either low or high grade dysplasia, or with superficial submucosal carcinoma). The presence of high grade dysplasia or superficial submucosal carcinoma may be suggested by an irregular vessel or surface pattern, and is often associated with atypical morphology (e.g., depressed area).

Figure 3. NICE classification.

	Type 1	Type 2A	Type 2B	Type 3
Vessel pattern	· Invisible ^{※1}	· Regular caliber · Regular distribution (meshed/spiral pattern) ^{※2}	· Variable caliber · Irregular distribution	· Loose vessel areas · Interruption of thick vessels
Surface pattern	· Regular dark or white spots · Similar to surrounding normal mucosa	· Regular (tubular/branched/papillary)	· Irregular or obscure	· Amorphous areas
Most likely histology	Hyperplastic polyp/ Sessile serrated polyp	Low grade intramucosal neoplasia	High grade intramucosal neoplasia/ Shallow ^{※3} submucosal invasive cancer	Deep submucosal invasive cancer
Endoscopic image				

*1. If visible, the caliber in the lesion is similar to surrounding normal mucosa.

*2. Microvessels are often distributed in a punctate pattern and well-ordered reticular or spiral vessels may not be observed in depressed lesions.

*3. Deep submucosal invasive cancer may be included.

Figure 4. JNET classification.

[figure not shown]

Figure 5. OCT imaging of normal colon tissue and colon cancer on left, corresponding pathology on right.

APPENDIX A: Definitions for Adverse Event Reporting

A. Adverse Events (AEs)

As defined in 21 CFR 312.32:

Definition: any untoward medical occurrence associated with the use of a drug in humans, whether or not considered drug-related.

Grading: the descriptions and grading scales found in the revised NCI Common Terminology Criteria for Adverse Events (CTCAE) version 5.0 will be utilized for all toxicity reporting. A copy of the CTCAE version 5.0 can be downloaded from the CTEP website.

Attribution (relatedness), Expectedness, and Seriousness: the definitions for the terms listed that should be used are those provided by the Department of Health and Human Services' Office for Human Research Protections (OHRP). A copy of this guidance can be found on OHRP's website:

<http://www.hhs.gov/ohrp/policy/advevntguid.html>

B. Suspected Adverse Reaction (SAR)

As defined in 21 CFR 312.32:

Definition: any adverse event for which there is a reasonable possibility that the drug caused the adverse event. "Reasonable possibility" means there is evidence to suggest a causal relationship between the drug and the adverse event. "Suspected adverse reaction" implies a lesser degree of certainty about causality than adverse reaction, which means any adverse event caused by a drug.

C. Life-Threatening Adverse Event / Life Threatening Suspected Adverse Reaction

As defined in 21 CFR 312.32:

Definition: any adverse drug event or suspected adverse reaction is considered "life-threatening" if, in the view of the investigator, its occurrence places the patient at immediate risk of death. It does not include an adverse event or suspected adverse reaction that, had it occurred in a more severe form, might have caused death.

D. Serious Adverse Event (SAE) or Serious Suspected Adverse Reaction

As defined in 21 CFR 312.32:

Definition: an adverse event or suspected adverse reaction is considered "serious" if, in the view of the investigator, it results in any of the following outcomes:

- Death
- A life-threatening adverse event

- Inpatient hospitalization or prolongation of existing hospitalization
- A persistent or significant incapacity or substantial disruption of the ability to conduct normal life functions
- A congenital anomaly/birth defect
- Any other important medical event that does not fit the criteria above but, based upon appropriate medical judgment, may jeopardize the subject and may require medical or surgical intervention to prevent one of the outcomes listed above

E. Protocol Exceptions

Definition: A planned change in the conduct of the research for one participant.

F. Deviation

Definition: Any alteration or modification to the IRB-approved research without prospective IRB approval. The term “research” encompasses all IRB-approved materials and documents including the detailed protocol, IRB application, consent form, recruitment materials, questionnaires/data collection forms, and any other information relating to the research study.

A minor or administrative deviation is one that does not have the potential to negatively impact the rights, safety, or welfare of participants or others or the scientific validity of the study.

A major deviation is one that does have the potential to negatively impact the rights, safety, or welfare of participants or others or the scientific validity of the study.

APPENDIX B: Reporting Timelines

Expedited Reporting Timelines		
Event	HRPO	QASMC
Unanticipated problem involving risk to participants or others	Report within 10 working days. If the event results in the death of a participant enrolled at WU/BJH/SLCH, report within 1 working day.	Report via email after IRB acknowledgment
Major deviation	Report within 10 working days. If the event results in the death of a participant enrolled at WU/BJH/SLCH, report within 1 working day.	
A series of minor deviations that are being reported as a continuing noncompliance	Report within 10 working days.	
Protocol exception	Approval must be obtained prior to implementing the change	
Complaints	If the complaint reveals an unanticipated problem involving risks to participants or others OR noncompliance, report within 10 working days. If the event results in the death of a participant enrolled at WU/BJH/SLCH, report within 1 working day. Otherwise, report at the time of continuing review.	
Breach of confidentiality	Within 10 working days.	
Incarceration	If withdrawing the participant poses a safety issue, report within 10 working days. If withdrawing the participant does not represent a safety issue and the patient will be withdrawn, report at continuing review.	

Routine Reporting Timelines		
Event	HRPO	QASMC
Adverse event or SAE that does not require expedited reporting	If they do not meet the definition of an unanticipated problem involving risks to participants or others, report summary information at the time of continuing review	Adverse events will be reported in the toxicity table in the DSM report which is typically due every 6 months.
Minor deviation	Report summary information at the time of continuing review.	
Complaints	If the complaint reveals an unanticipated problem involving risks to participants or others OR noncompliance, report within 10 working days. If the event results in the death of a participant enrolled at WU/BJH/SLCH, report within 1 working day. Otherwise, report at the time of continuing review.	
Incarceration	If withdrawing the participant poses a safety issue, report within 10 working days.	

Routine Reporting Timelines		
Event	HRPO	QASMC
	If withdrawing the participant does not represent a safety issue and the patient will be withdrawn, report at continuing review.
